5.7 OTHER ANALYSES

5.7.1 Summaries of Conduct of Study

Eligibility criteria deviations and other major Protocol deviations will be tabulated in the ITT Population and a listing will be provided. Summaries of duration of study follow-up will be provided for the ITT Population through Week 52 at the primary analysis and through end of study for the final analysis.

The impact of COVID-19 on data integrity will be assessed in terms of the following criteria:

- Discontinuing study treatment (PDS arm) or discontinuing study (comparator arm) due to COVID-19
- Missed treatments due to COVID-19 or related precautions
- Use of prohibited therapy due to COVID-19
- Missing ETDRS-DRSS assessments due to COVID-19 or related precautions
- Missing BCVA or BCVA not performed per Protocol due to COVID-19 or related precautions
- Major Protocol deviations associated with COVID-19 directly or indirectly
- Missed visits reported as due to COVID-19 or related precautions
- Early study discontinuation due to COVID-19
- Death due to COVID-19
- Confirmed or suspected cases of COVID-19 and AEs associated with COVID-19

Pre-treatment and concomitant systemic medications, ocular medications for the fellow eye, and ocular medications for the study eye will be summarized separately by treatment group in the in the Safety-Evaluable Population through Week 52 at the Primary Analysis and in the PDS Safety Population through End of Study. Listings of anti-VEGF treatment in the study eye following explantation and of anti-VEGF treatment in the fellow eye will be provided in the Safety-Evaluable Population.

5.7.2 Summaries of Treatment Group Comparability

Summaries by treatment arm for clinically important demographic and baseline characteristics will be provided in the ITT Population and in the PDS Safety Population. The variables will be summarized using means, SDs, medians, and ranges for continuous variables and proportions for categorical variables. The baseline summary will include:

- Age
- Sex
- Race
- Disease characteristics (duration of diabetes, type of diabetes, HbA1c, ETDRS-DRSS, BCVA, CST, etc.)

5.7.3 Pharmacokinetic Analyses

PK analyses will be performed in the PDS PK Population, PDS PK–Evaluable Population, and Aqueous Humor PK Evaluable Population (see Section 4).

Summaries of ranibizumab concentration data will be tabulated for each of the PK populations defined. Median serum ranibizumab concentration-versus-time data will be plotted in the PDS PK and PDS PK–Evaluable Populations. Summaries of ranibizumab concentration at the time of supplemental intravitreal ranibizumab treatment and subsequent treatment may be generated. Aqueous humor ranibizumab concentration data will be tabulated and plotted in the Aqueous Humor PK Evaluable Population.

Due to the sparse serum PK samples collected in the study, the AUC, C_{max} and t_{max} of ranibizumab cannot be obtained using observed data. The observed ranibizumab serum C_{min} by group will be tabulated and summarized (mean, SD, coefficient of variation, median, and minimum and maximum) by descriptive statistics. Between-patient variability will be evaluated.

Exploratory PK analyses to evaluate potential relationships between drug exposure and efficacy and safety of the PDS may be performed, as applicable.

5.7.4 Immunogenicity Analyses

The immunogenicity analysis population will include all patients with at least one ADA assessment. Baseline ADA prevalence will be estimated based on sample collected at the time of randomization; patients will be grouped according to treatment received or, if not treatment is received prior to study discontinuation, according to treatment assigned.

The immunogenicity incidence will be summarized according to treatment received prior to Week 52. ADA samples will be collected prior to dosing during the randomization visit and at Weeks 4, 8, 28, 52, 64, 76, and 112 in the PDS arm and during the randomization

visit and at Weeks 60, 64, 68, 88, and 100 in the comparator arm and at early termination or explant visit in both arms.

ADA incidence (number and percentage) will be summarized as follows in the PDS Population for the primary analysis at Week 52 and through the entire study at the final analysis:

- Pre-implant ADA incidence: at the last measure prior to implant (the reference visit)
- Post-implant ADA incidence: at any time after implant based on patients in the PDS
 Safety Population who have ADA samples at the reference visit and after implant:
 - a) PDS patients who were ADA negative at the reference visit and are with at least one positive result after implant. These patients are considered to have treatment-induced ADA responses.
 - b) PDS patients who were ADA positive at the reference visit and ADA titer increased after implant; in this case, the titer results of one or more samples collected after implant are at least 0.60 titer units greater than the titer result of the reference visit sample. These patients are considered to have treatmentenhanced ADA responses.

The combined rates described in (a) and (b) above will provide the incidence of patients positive for treatment-emergent ADAs. Patients are considered to be negative for Treatment-emergent ADAs if they are ADA negative at all timepoints after the reference visit. Patients are also considered to be Treatment unaffected for ADAs if they are ADA positive at the reference visit and (a) where all post-baseline titer results are less than 0.60 t.u. greater than the titer result of the reference visit, OR (b) where all post-baseline results are negative or missing. A listing of patients with positive serum antibodies to ranibizumab will be provided.

The immunogenicity assessment will also include testing for the presence of neutralizing antibodies in samples confirmed to be positive for anti-ranibizumab antibodies. The incidence of neutralizing antibodies will be grouped and reported in a similar fashion to that described above.

The relationship between ADA status and safety, efficacy, PK, and biomarker endpoints may be explored.

5.7.5 Biomarker Analyses

Biomarker analyses will be performed on the Aqueous Humor Biomarker Evaluable Population at the time of the Final Analysis. No biomarker analyses are planned at the Primary Analysis. Descriptive summaries of aqueous humor free VEGF concentration (original and log-transformed) and change in concentration from baseline will be tabulated and plotted by visit and by treatment arm.

The mean change from baseline in Free-VEGF log concentrations in the PDS arm at week W28 will be presented with a 95% CI.

The difference in the mean change from baseline in Free-VEGF fold change at W28/W24 between PDS and comparator arms respectively will be presented with a 95% CI.

Data after PDS implant from patients in the Aqueous Humor PK Population in patients with at least one post-implant Aqueous Humor PK sample will be summarized descriptively by treatment arm and overall.

Sensitivity analysis may be performed with the population that excludes patients who receive supplemental treatment.

Additional exploratory biomarker analyses to evaluate potential relationships between free VEGF, drug exposure, disease severity, and/or efficacy of the PDS will be performed, as applicable.

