1.1.3 Pharmacokinetic Objectives

The pharmacokinetic (PK) objective for this study is to characterize the serum PK profile of ranibizumab 100 mg/mL delivered via the PDS after the initial implant insertion and subsequent refill-exchange procedures in patients with DR on the basis of the following endpoints:

- Serum concentration of ranibizumab observed over time
- Additional estimated PK parameter values, including area under the concentration-time curve (AUC), maximum serum concentration (C_{max}), minimum serum concentration, and half-life (t_{1/2}) after PDS implant insertion

The exploratory PK objectives for this study are to evaluate potential relationships between drug exposure and the efficacy and safety of ranibizumab and to characterize ranibizumab aqueous humor concentration over time delivered via the PDS on the basis of the following endpoints:

- Relationship between serum concentration or PK parameters for ranibizumab delivered via the PDS and efficacy endpoints
- Relationship between serum concentration or PK parameters for ranibizumab delivered via the PDS and safety endpoints
- Measured aqueous humor concentrations of ranibizumab over time

1.1.4 Immunogenicity Objectives

The immunogenicity objective for this study is to evaluate the immune response to ranibizumab 100 mg/mL delivered via the PDS on the basis of the following endpoint:

- Prevalence of anti-drug antibodies (ADAs) prior to study treatment and incidence of ADAs after study treatment
- Prevalence of neutralizing antibodies at baseline and incidence of neutralizing antibodies during the study

The exploratory immunogenicity objective for this study is to evaluate potential effects of ADAs and neutralizing antibodies on the basis of the following endpoint:

 Relationship between ADA status, neutralizing antibodies and efficacy, safety, or PK endpoints

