Patients randomized to the PDS arm will receive at least two loading doses with intravitreal ranibizumab 0.5 mg injections, administered at Day 1 and Week 4 visits. The first loading dose must be administered after the conclusion of the randomization visit assessments. At Week 4, patients must complete a pre-implant visit prior to the implant insertion surgery. Both visits must be completed within the Week 4 window and the PDS implant (pre-filled with ranibizumab 100 mg/mL) will be surgically inserted 1-14 days after the second loading dose (e.g., if the patient receives the second loading dose at Day 28 (Week 4), implant insertion surgery must occur no earlier than Day 29 and no later than Day 35). Patients will receive PDS implant refill-exchange procedures (ranibizumab 100 mg/mL) at Weeks 40, 76, 112, and Q36W thereafter (Visit Z refill-exchange visit) until the end of the study.

Patients in the PDS arm who meet specific clinical criteria (development of CI-DME or PDR/ASNV) per Investigator assessment can receive supplemental treatment with intravitreal ranibizumab 0.5 mg injections per Investigator's clinical judgment at any non–refill-exchange study visit during the study post implant (see Section 4.3.2.3 of the Protocol).

Patients randomized to the comparator arm will undergo study visits every 4 weeks (Q4W) for observation and comprehensive clinical monitoring. Beginning at Week 60, patients will receive two loading doses with intravitreal ranibizumab 0.5 mg injections, administered at the Week 60 and Week 64 visits. At Week 64, patients must complete a pre-implant visit prior to the implant insertion surgery. Both visits must be completed within the Week 64 window and the PDS implant (pre-filled with ranibizumab 100 mg/mL) surgically inserted 1-14 days after the Week 64 intravitreal injection. Patients will undergo a refill-exchange procedure with ranibizumab 100 mg/mL at Week 100 and Q36W thereafter (Visit Z refill-exchange visit) until the end of the study.

If PDS implant insertion surgery cannot be completed within the required timeframe (1-14 days after intravitreal ranibizumab 0.5 mg injection and within the study visit

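### Pre-implant ADA incidence in SAP Section 5.7.4 is a prevalence at the reference visit, because antibodies already present at randomization are counted as incident; two of the post-implant ADA classes also overlap

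*SAP*

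**What the plan says.** Section 1.1.4 sets two different measures: "Prevalence of anti-drug antibodies (ADAs) prior to study treatment and incidence of ADAs after study treatment". Section 5.7.4 implements the first from one sample: "Baseline ADA prevalence will be estimated based on sample collected at the time of randomization".

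The second measure is split at implantation. The pre-implant part is "Pre-implant ADA incidence: at the last measure prior to implant (the reference visit", with no further condition. The post-implant part requires a change from that reference visit. It is either (a) a positive result in a reference-negative patient or (b) a titer at least 0.60 units above the reference in a reference-positive patient. The sum of (a) and (b) is the treatment-emergent rate.

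Section 5.7.4 then adds two classes of patients who are not treatment-emergent. The first reads: "Patients are considered to be negative for Treatment-emergent ADAs if they are ADA negative at all timepoints after the reference visit". The second, *treatment unaffected*, covers reference-positive patients without a titer rise of 0.60, or those "where all post-baseline results are negative or missing".

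For the PDS arm, "ADA samples will be collected prior to dosing during the randomization visit and at Weeks 4, 8, 28, 52, 64, 76, and 112". The comparator arm is sampled at the randomization "visit and at Weeks 60, 64, 68, 88, and 100 in the comparator arm". Section 1.2 gives PDS patients "at least two loading doses with intravitreal ranibizumab 0.5 mg injections, administered at Day 1 and Week 4 visits", with implantation after the Week 4 dose. Neutralizing antibodies are to be reported in a similar fashion, so the same rules carry over to them.

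**The concern.** Incidence needs a starting state and a change from it. The post-implant rule has both and the pre-implant rule has neither: it records status at one visit. The label then says something the definition does not deliver, and the result conflicts with the prevalence and incidence split in Section 1.1.4.

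The line matters because it is the only planned incidence line that can show antibodies arising during the loading phase. A patient who converts after the first injection and stays positive without a titer rise is *treatment unaffected* after implantation and does not enter (a)+(b). If the pre-implant line mixes that patient with patients who were positive before any study drug, no tabulated rate isolates conversion after loading.

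A second, smaller problem is that the emergent-negative rule places no condition on the reference result, while the unaffected rule is reserved for reference-positive patients. One patient can therefore satisfy both.

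**Working it through.** **Inputs from the SAP.** Baseline prevalence comes from the pre-dose randomization sample (Section 5.7.4). On schedule, the reference sample is Week 4 in the PDS arm, after at least the Day 1 loading dose. In the comparator arm it is Week 64, after the Week 60 dose (Sections 1.2 and 5.7.4). The SAP states no ADA rate, so there is no planned figure to reproduce.

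**Step 1: what each line requires.**

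| Line in Section 5.7.4 | Starting state | Change required |
|---|---|---|
| Baseline prevalence | none | none |
| Pre-implant incidence | none | none |
| Post-implant (a) | reference negative | becomes positive |
| Post-implant (b) | reference positive | titer rise of at least 0.60 |

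The pre-implant line has the structure of the prevalence line, not of the incidence lines below it.

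**Step 2: size, under assumptions.** Let p0 be positivity at randomization and i the probability that a patient negative at randomization is positive at the reference visit. Assume positives persist to the reference visit. Then:

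- reported value = p0 + i(1 − p0)
- new-onset value = i(1 − p0)
- excess = p0
- pre-existing share = p0 / [p0 + i(1 − p0)]

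| p0 | i | Reported per 100 | New onset per 100 | Pre-existing share |
|---|---|---|---|---|
| 1% | 0% | 1.00 | 0.00 | 100% |
| 1% | 1% | 1.99 | 0.99 | 50% |
| 1% | 3% | 3.97 | 2.97 | 25% |
| 3% | 1% | 3.97 | 0.97 | 76% |
| 5% | 1% | 5.95 | 0.95 | 84% |
| 10% | 3% | 12.70 | 2.70 | 79% |

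For example, with p0 = 5% and i = 1%: 0.05 + 0.01 × 0.95 = 0.0595, against 0.01 × 0.95 = 0.0095. The third and fourth rows give the same reported figure, 3.97, from new-onset values of 2.97 and 0.97, so the planned number cannot tell them apart. Over p0 from 1% to 10% and i from 0% to 3%, the pre-existing share runs from 25% to 100%. If some early positives lose positivity before the reference visit, the excess is smaller than p0. If a titer rise from randomization is also counted as incident, some of the p0 patients would rightly stay in; the SAP does not allow that part to be quantified.

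**Step 3: the classes, read literally.**

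| Randomization / reference / after implant | Pre-implant line | Post-implant label |
|---|---|---|
| + / + / all negative | counted | emergent-negative **and** unaffected |
| − / + / all negative | counted | emergent-negative **and** unaffected |
| + / + / positive, no rise | counted | unaffected |
| − / + / positive, no rise | counted | unaffected |
| + / + / rise of 0.60 or more | counted | in (a)+(b) |
| − / − / all negative | not counted | emergent-negative |
| − / − / any positive | not counted | in (a)+(b) |

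The first two rows carry two labels, but neither label is part of (a)+(b), so the treatment-emergent rate does not move.

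The term post-baseline in the unaffected rule has no stated anchor. If baseline means randomization, as it does for prevalence, the positive reference sample is itself post-baseline, and the branch requiring all results negative or missing could never be met. The rule works only if the term means after the reference visit.

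**The case against.** The best reply is that this is a label and not a hidden rule. The line says openly that it is status at the last pre-implant measure. Randomization prevalence is reported beside it, and positive patients are listed. A careful reader could separate most old cases from new ones. That is true of the listing, but the tabulated rate stays mislabelled. Subtracting one rate from the other works only if all early positives persist and both rates share a denominator.

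Three stronger readings are tempting, and the SAP does not support them.

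- A reader might infer from the words on missing results that patients never sampled after implantation are called *treatment unaffected*. Section 5.7.4 limits post-implant incidence to patients with samples at the reference visit and after implant. Within that group, missing most naturally means individual missed samples. The limit should be repeated for the classes, but it is not absent.
- A reader might infer that the overlapping classes corrupt the treatment-emergent rate or a total. They do not change (a)+(b), and the SAP neither calls the classes mutually exclusive nor promises a table in which they sum. The word also, introducing the second class, can be read as adding another way of being non-emergent.
- A reader might infer that most pre-implant positives will be pre-existing. That depends wholly on the assumed p0 and i, and the range above includes a share as low as 25%.

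It also stands that the output is descriptive, and that relating ADA status to other endpoints is optional in the SAP.

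**Conclusion.** The point holds as a defect in a descriptive safety output. The rule as written yields a prevalence at the reference visit and reports it as incidence, contrary to Section 1.1.4. Every patient positive at both randomization and the reference visit is counted as incident without any evidence of change. If positives persist and titer rises are set aside, the excess equals the prevalence at randomization; both that rate and the new-onset rate are assumptions here. The class overlap is real but confined to reference-positive patients who are negative throughout afterwards, and it leaves the treatment-emergent rate unchanged. The primary analysis, the type I error and the sample size are not affected. The change is worth making because the correct rate can be had from samples already planned.

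**What to change.** In Section 5.7.4:

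1. Define pre-implant ADA incidence against the randomization sample: negative at randomization and positive at a later pre-implant sample, or a titer rise of at least 0.60 units from randomization. State that patients need both a randomization and a later pre-implant sample.
2. Report status at the reference visit under the name pre-implant prevalence.
3. Limit the emergent-negative class to patients who were negative at the reference visit.
4. Replace post-baseline in the unaffected rule by after the reference visit.
5. State that all post-implant classes apply only to patients with at least one post-implant result, and keep the allowance for missing results only for individual missed samples.
6. Apply the same wording to neutralizing antibodies where it fits.

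The cost is SAP wording and one changed derivation. No new samples or visits are needed. The reported pre-implant incidence will normally be lower, and the figure now planned is kept under its proper name.
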